### 7.2 AIMS: List the specific aims:

**Specific Aim 1:** To refine and manualize an 8-week **MBPR (Mindfulness-Based Pain Reduction)** program for patients with cLBP, integrating mindfulness with (1) interoceptive awareness, i.e. cultivating a direct, non-judgmental sensory attention focus on the location of their cLBP, (2) yoga practices targeting cLBP, and (3) elements of both chronic pain education and CBT, i.e., modifying maladaptive cognition and behavior. In Phase 1 we are convening a panel of behavioral and yoga therapists with expertise in chronic pain education and management to obtain expert advice on MBSR optimization and produce a first draft of the new MBPR manual.

**Specific Aim 2:** To refine **ecological momentary assessments (EMA) measures of key pain outcomes and mobile technology measures of adherence to MBPR home practice.** EMA is emerging as a key tool for measuring pain outcomes and home practice in clinical trials, but measures are poorly standardized and validated. We will compare pain questionnaires and EMA and ensure that an EMA measure is refined and vetted before use as a clinical trial outcome. We will test a meditation timer mobile app to measure adherence.

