## **done solely for research purposes and those that are happening as part of routine care.**

Please call our office at [contact] and ask to speak to someone on the Expedited Review team if you need help differentiating between what parts are research and what parts aren't.

At UCSF:

As we described in the application for Phase 1 of this study, **MBSR** is a standardized and manualized 8-week program, delivered once a week in 2½-hour group sessions and a daylong retreat. It trains individuals in several mindfulness practices, e.g. focus on breath, varying degrees and directions of object orientation, open monitoring of awareness of intero- and exteroceptive stimuli and thoughts, de-reification (i.e. the notion that thoughts and perceptions are not always true to reality), and meta-awareness (i.e., awareness of thinking) in addition to focused attention. The program typically includes an audio-recording and a book for home practice and has shown benefits in patients with cLBP.

**MBPR** will be an optimized mindfulness program specifically designed for treating cLBP that we aim to develop and test in this project. The format is the same as MBSR: 8 weeks of weekly 2½-hour group sessions and a daylong retreat in smaller groups: 10 participants per class to allow for more individualized support. All sessions include training to enhance mindful interoceptive awareness through focused attention in the region of pain, the lower back. Key goals are to reduce avoidance, rumination, catastrophizing, and fear of movement, all key mechanisms of action in MBSR or CBT. The new elements of these classes will include more pain-specific education and key elements of CBT, enhance mindful interoceptive awareness and an expanded yoga component, for which we will provide videos for home practice.

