**Meditation home practice adherence measure:** *Rationale:* All participants will be instructed to do daily home practice. Benefits of any mind-body intervention may depend on applying the class teaching to practice at home. Home practice for chronic conditions may need a higher dose than e.g. for experimental pain. We will request a minimum of 30 minutes for an expected effective duration of 20 minutes (>70%) on at least 5 days per week. *Methods:* Our research team has successfully used the free downloadable mobile app InsightTimer® to monitor adherence to home practices by asking participants to use it during home practice session. It has a variety of bell sounds that can be set for desired meditation time periods. The application includes two other features we have successfully tested at UCSF: 1) It connects with the research team in our study providing data about when and for how long a participant practiced meditation. 2) The app allows guided meditation recordings that we are preparing for home practice to be uploaded and made available to participants. Participants will log in with unique pseudonyms and a participant-specific e-mail address that is created for this study only to eliminate any risk to loss of privacy, which will be discussed during the consent process. Any identification of the

participating InsightTimer user will not be possible as the app will not use the personal e-mail of the participant and only use pseudonyms.

At the VA:

This study includes a Pain Attention Task to be preformed in the fMRI that separates insula activation during experimental heat application between different pain attention conditions.

The participants will be patients with cLBP according to the definition of the NIH Task Force on Research Standards for cLBP: pain at least half the days in the past 6 months, by using 2 questions and a human figure drawing illustrating the region between the lower posterior margin of the rib cage and the horizontal gluteal fold. Participants will have an average pain intensity in the past week of at least 4 out of 10 on the numeric rating scale (NRS). They will be recruited through advertisement in newspapers, social media and fliers, and from the current UCSF Spine Center cLBP cohort (see below).

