## 4 EXPECTED RISKS

- 4.1 Behavioral / Psychological Questionnaires:** These carry a minimal risk for emotional discomfort and stress.
- 4.2 Post-Intervention Interviews:** These carry a minimal risk for emotional discomfort and stress.
- 4.3 Privacy:** Participating in the study may result in a loss of privacy because the intervention is administered in a group setting. Participants will be asked not to share information related to other individuals when they are outside of class, but this cannot be guaranteed. Questionnaires will include background medical information and psychological scales and all research data will be stored on the secured web-based Research Electronic Data Capture (REDCap) and Qualtrics systems. Subjects are informed that they are free to refuse to participate in any stage of the work and can refuse to answer specific questions or questionnaire items if they wish.
- 4.4 Unexpected Events:** A physician is present or on call during all study procedures, and will be available if a participant experiences suicidal ideation or other mental health problem. All subjects will be provided with contact numbers in case distress arises following the experiment or intervention.

**4.5 Yoga-type movements and postures as a component of MBPR/MBSR:** Yoga has been found to be relatively safe in a number of large-scale randomized trials however any exercise program may result in muscle soreness or strains. Adverse events do occasionally occur and it is important that participants report any injuries to study staff. To improve safety, all participants will complete a pre-intervention assessment.

Prior to the start of MBPR/MBSR classes participants will be evaluated to determine if their pain worsens with flexion or extension. We will monitor pain levels during physical exercises. Classes are much smaller than common MBSR classes (10 participants instead of 15-25) and instructors are better able to help participants with individual adjustments and advice.

Finally, for those doing yoga-type exercises and postures, several minor adverse effects may occur and include increased low back pain intensity, muscle strain or sprain, or dizziness and are generally of short duration and alleviated by local physical measures (such as ice) and physical rest. They will be thoroughly addressed in the intervention.

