**4.6 Fluctuations in Pain Levels:** Study physician [name] will weekly review the class reports and videos. He will be available by cell phone for more urgent problems between in-person consultations. Primary care physicians for each participant will receive information about the study before the participant begins the study. Study physician will help to make sure that primary care physicians are informed of any medical changes, and will consult with primary care physicians where indicated.

**4.7 MBPR and MBSR:** Similar interventions have been used with thousands of persons, including many with serious illness and pain conditions, and there have not been important adverse events reported to our knowledge. Participants can experience restlessness during the meditation practices or become aware of distressing emotions and traumatic memories. Our instructors are highly trained and experienced and will immediately inform the study physician, who will determine whether referral to behavioral medical care is warranted.

**4.8 Home Exercise Components:** Participants will be requested to do yoga-style exercises at home. Some people may experience initial discomfort when increasing their level of physical activity. There may also be a slight increase for physical risks when partaking in exercise activities. There are minor risks of injury during exercise, but these risks are minor and far out-weighed by the potential benefits of exercise.

**4.9 Audio/Video-Taping Instructors During Classes:** classes will be audio-videotaped to ensure intervention fidelity and provide feedback and troubleshooting for instructors. Some participants may experience a level of discomfort while being recorded during class. Although the recorders will be placed in front of the class to record the instructors' voice, there is a strong likelihood that some of the participants' movements and voices will be recorded. They may also feel that they are being monitored. Participants will be informed of the recording, and can sit farther from the microphone if they desire. Recordings will be kept on a HIPAA-compliant research network drive with password-restricted access limited to study staff. Recordings will be destroyed once the study is complete. Adverse event/unanticipated problems

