## 15.0 Financial Considerations

**15.1 \* PAYMENT:** Will subjects be paid for participation, reimbursed for time or expenses, or receive any other kind of compensation: **(REQUIRED)**

- Yes
- No

**15.2 PAYMENT METHODS:** Subjects payment or compensation method (check all that apply):

Payments will be (check all that apply):

- Cash
- Check
- Gift card
- Debit card

UCSF Research Subject Payment Card  
 Reimbursement for parking and other expenses  
 Other:

**15.3 PAYMENT SCHEDULE: Describe the schedule and amounts of payments, including the total subjects can receive for completing the study:**

- If there are multiple visits over time, explain how payments will be prorated for partial completion
- If deviating from recommendations in Subject Payment Guidelines, include specific justification below

In return for their time, effort, and travel expenses, participants will be paid \$100 per visit at the San Francisco VA Medical Center, plus \$15 travel reimbursement, in the form of a check or a gift card. Participants will receive \$1.00 for each smart phone response during weeks 1 and 8 of the classes (up to \$40). They will receive \$50 each time after completing the questionnaires at 8 weeks and 6 months (up to \$100). If participants take part in the exit interview they will be paid \$100. The total payment amount will be up to \$440 plus up to \$30 for travel expenses. This is the total amount and includes the amount for the study activities at the VA. Participants will be reimbursed for time when undergoing fMRI for each of two visits (\$100 per visit) and up to \$15 for travel and parking expenses for each visit.

Timing of payment: VA visits at the end of the visit; smart phone responses and 8 week questionnaire after responding to questionnaire; 6-month questionnaire after responding to the questionnaire.

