Are the assessments too burdensome?	Proportion of planned pre- and post-intervention assessments completed, duration of assessments, and quantitative and qualitative participant feedback.
Are the treatment conditions acceptable to participants?	Acceptability ratings; qualitative participant assessments; reasons for dropouts.
Are the treatment conditions credible?	Perceived benefit at end course and likelihood of recommending to a friend or family member (net promoter score) at the end of the course during randomized phase.
Is EMA assessment of pain intensity/interference feasible?	Proportion of EMA assessments responded to (we hypothesize that this will be > 80%). Qualitative data on acceptability.
Is assessment of meditation adherence with app feasible?	Correlation of meditation sessions measured with Insight Timer with self-report of practice during the same week; qualitative interviews.

Hypothesis 3: MBPR participants will improve in key pain outcomes. Our planned primary outcome measures in future trials will be pain interference (RTF) and pain intensity (NRS); pain acceptance and quality of life will be secondary outcomes. We will conduct exploratory hierarchical linear modeling¹⁵⁵ to examine the extent to which participants experience changes in pain interference at the end of the intervention and at 6-month follow-up (separate for EMA and questionnaires). For both pain outcome variables (pain interference, pain intensity) separate multilevel models will be estimated. The pain measure models will take into account that the present data set is organized within three different levels and that single observations (i.e., rating at a particular time during the day)(Level 1) are nested within days (i.e., rating on day 1-7 in week 1 or 8 of intervention)(Level 2), which are nested in variations of MBPR per

course (Level 3). As this is not an efficacy study, we will primarily report standardized effect sizes (Cohen-*d*) with 95% confidence intervals, based on standard deviation at baseline. Similar models for secondary outcomes will include pain acceptance, and quality of life as outcomes, each in a separate correlation.

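### The earliest timed EMA week falls inside the course, so the EMA reference level for the exploratory Hypothesis 3 change is at least partly on treatment

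*SAP*

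**What the plan says.** **EMA timing.** SAP Hypothesis 3 defines the day level of its EMA model as "rating on day 1-7 in week 1 or 8 of intervention". Protocol 15.3 pays $1.00 "for each smart phone response during weeks 1 and 8 of the classes", up to $40. The Schedule of Measures in Protocol 7.9 refers forward to EMA details, but no timing follows, and the instrument list in 7.11 gives EMA no time point. The SAP also plans an EMA change at 6 months, for which no window or payment is described.

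**Effect size.** Hypothesis 3 reports Cohen's d "based on standard deviation at baseline". It does not define baseline for EMA.

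**Content of week 1.** MBPR has one group session a week for 8 weeks (Protocol 7.9). "All sessions include training to enhance mindful interoceptive awareness through focused attention in the region of pain, the lower back". On home practice, 7.9 says: "All participants will be instructed to do daily home practice". No start day is given.

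**Possible early discomfort.** DSMP 4.5 says of yoga-type exercises that "several minor adverse effects may occur and include increased low back pain intensity". DSMP 4.8 says of home exercise: "Some people may experience initial discomfort when increasing their level of physical activity".

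**Questionnaires.** Protocol 7.9 places them in the first and last course weeks. Protocol 10.14 lists the first round ahead of the orientation and classes. The SAP feasibility table speaks of pre-intervention assessments without naming an instrument.

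**The concern.** A pre-to-post change needs a reference level from before treatment. For EMA, the earliest ratings with a stated time come from the week in which treatment begins. If pain eases early, the week-1 mean already holds part of the benefit and the EMA change is understated. If unfamiliar movement raises pain at first, the week-1 mean is too high and the change is overstated. The trend within week 1 can be inspected, but the untreated level cannot be recovered unless some EMA days precede class 1.

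The immediate stake is modest, since Hypothesis 3 is exploratory and the study disclaims efficacy. The longer-term stake is that Aim 2 (Protocol 7.2) exists to "ensure that an EMA measure is refined and vetted before use as a clinical trial outcome". A window adopted here may be carried into the later MBPR-versus-MBSR trial.

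**Working it through.** **1. Is there room for another paid EMA week?** From Protocol 15.3: 2 × $100 (MRI) + $40 (EMA) + 2 × $50 (questionnaires) + $100 (interview) = $440. This equals the stated maximum before travel, so no paid EMA lies outside weeks 1 and 8.

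**2. How much of week 1 is exposed?** If class 1 falls on EMA day k, then 8 − k of the 7 EMA days are on or after it, which is 7 (k = 1) down to 1 (k = 7). The documents do not give k.

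**3. Early benefit only.** The documents give no response curve and no EMA standard deviation, so everything here is assumed. Let r(t) be the share of the response reached t weeks after class 1, with r = 0 before it. Take r(t) = t/8 (linear) or r(t) = 1 − 2^(−t/h) with half-life h = 3, 2 or 1 weeks. With c = (k − 1)/7:

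- W1 = mean of r(x − c) over weeks 0 to 1
- W8 = mean of r(x − c) over weeks 7 to 8
- share of the change lost = W1/W8
- observed d = 0.50 × (1 − W1/W8), for an assumed true d of 0.50

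| Class 1 on EMA day | Quantity | Linear | h = 3 | h = 2 | h = 1 |
|---|---|---|---|---|---|
| 1 | W1 | 0.0625 | 0.1071 | 0.1549 | 0.2787 |
| 1 | W8 | 0.9375 | 0.8228 | 0.9253 | 0.9944 |
| 1 | lost | 6.7% | 13.0% | 16.7% | 28.0% |
| 1 | observed d | 0.47 | 0.43 | 0.42 | 0.36 |
| 4 | W1 | 0.0204 | 0.0361 | 0.0530 | 0.0996 |
| 4 | W8 | 0.8839 | 0.8044 | 0.9133 | 0.9924 |
| 4 | lost | 2.3% | 4.5% | 5.8% | 10.0% |
| 4 | observed d | 0.49 | 0.48 | 0.47 | 0.45 |
| 7 | lost | 0.15% | 0.30% | 0.39% | 0.69% |

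**4. Add an early flare.** Let a share p of people have a rise of s points for D days in week 1 and none in week 8. The week-1 mean rises by F = p × s × D/7. With a true change of 1.0 point and SD 2, observed/true = 1 − W1/W8 + F.

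| Flare | F | Class 1 on day | Linear | h = 3 | h = 2 | h = 1 |
|---|---|---|---|---|---|---|
| p = 0.2, s = 1, D = 3 | 0.086 | 1 | 1.02 | 0.96 | 0.92 | 0.81 |
| same | 0.086 | 4 | 1.06 | 1.04 | 1.03 | 0.99 |
| p = 0.4, s = 2, D = 3 | 0.343 | 1 | 1.28 | 1.21 | 1.17 | 1.06 |
| same | 0.343 | 4 | 1.32 | 1.30 | 1.29 | 1.24 |

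**5. Standard deviation.** SD = √(4 + p(1 − p)(s × D/7)²) gives 2.007 and 2.044 against 2.00. The ratios 2/SD are 0.996 and 0.979, so d falls by 0.4% or 2.1%.

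**6. Against sampling error.** In steps 3 and 4, the shift in d runs from 0.36 − 0.50 = −0.14 (day 1, h = 1, no flare) to 0.50 × 1.32 − 0.50 = +0.16 (day 4, linear, larger flare, before the SD effect). The approximate 95% half-width is 1.96 × √(2(1 − ρ)/40 + 0.50²/78). With the 40 MBPR participants, this is 0.33 for an assumed pre-post correlation ρ = 0.5 and 0.26 for ρ = 0.7.

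**The case against.** The strongest reply is that the EMA schedule is incompletely written and not shown to be wrong. The SAP wants an EMA change at 6 months, so a reader who infers that EMA is collected solely in weeks 1 and 8 goes further than the text. That stands. However, a 6-month window comes after the course and cannot supply a baseline.

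Second, the stated EMA purposes do not need an untreated reference. Aim 2 compares EMA with questionnaires, Hypothesis 4 predicts a correlation above 0.7, and the response target is above 80%. On the schedule in 7.9, EMA and questionnaires already share the first and last course weeks. That stands too: moving EMA alone would break the pairing.

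Third, every size above is assumed. The −0.14 end needs half the eventual benefit within a week of a day-1 class and no flare. The +0.16 end needs a sizeable flare in 40% of people. DSMP 4.5 does not confine increased pain to the start of the course, and an equal flare in week 8 would cancel the flare term. All of this stands, and it is why no direction of bias can be claimed.

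What does not stand is that the exploratory label or the wide interval removes the point. The interval describes sampling error. It does not cover a shift caused by when the reference is measured.

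**Conclusion.** The point holds as a limited one. The EMA reference level for the Hypothesis 3 change is at least partly on treatment, to a degree set by the unstated weekday of class 1. With no flare, the understatement is about 7% (linear) to 28% (1-week half-life) for class 1 on day 1, 2% to 10% on day 4, and under 1% on day 7. With an early flare the sign can reverse. All shifts fall inside the sampling interval of an exploratory estimate.

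Four stronger readings are tempting but unsupported:

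- **That the EMA effect will be understated.** The direction is unknown.
- **That the variance estimates for the next trial are spoiled.** The assumed flares move the SD by about 2% at most, and the SAP does not say which SD scales the EMA change.
- **That the questionnaire baseline is also on treatment.** Protocol 7.9 and 10.14 leave its timing ambiguous, and the SAP feasibility table does not settle it.
- **That all of week 1 is treated.** If class 1 falls late in the week, most ratings precede it.

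**What to change.** Treat this as a cheap improvement.

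1. In Protocol 15.3 and SAP Hypothesis 3, make the first EMA week the 7 days before class 1, with the same prompts and the same $40 cap. Keep week 8 as it is.
2. In the Schedule of Measures (7.9), state that baseline questionnaires are completed before class 1 and in that same EMA week. This removes the timing ambiguity and keeps the same-week pairing for Hypothesis 4.
3. Set up phones at a check-in call (10.14) or at the movement evaluation that precedes both programs (DSMP 4.5).

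**Cost.** Phone set-up comes about a week earlier, and a few people will be paid for EMA and then not start. If half of the $40 falls in each EMA week and 10% of 50 do not start (both assumed; the 10% is borrowed from the loss-to-follow-up contingency in DSMP 6.2), that is 5 × $20 = $100. The larger burden is procedural. Unless the change counts as minor and administrative, DSMP section 2 sends the amendment to NCCIH first and to the IRB only after NCCIH approval.

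**If the window cannot move.** Report the estimate as a week 1 to week 8 change scaled by the week-1 SD, not as change from baseline. Record the class-1 date against the EMA days. This needs only wording and one recorded date.

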Hypothesis 4: Assessment of pain intensity/interference with a smartphone delivered EMA is feasible and correlates with standard pain outcome measures. Feasibility/acceptability measures are noted in the table above. We will assess the correlation of our EMA measures with the Numeric Pain Rating Scale for pain intensity, and pain interference rating. We predict a correlation of >.7. We will also perform qualitative assessment to get participants assessment of where the two approaches are similar, and where they may get differing responses.

Hypothesis 5: Assessment of meditation practice adherence is feasible using a smartphone app. At the 8-week assessment period, we will include questions about meditation practice over the prior week and compare this with the results from use of the Meditation Insight Timer data. We will ask further questions about any sessions that were not recorded using the app, and reasons for not recording. This information will be analyzed after each group, and refinements made if needed in participant instructions and other steps to encourage use of the app as consistently as possible.

Hypothesis 6: We will conduct **exploratory analyses** to test for correlations between changes in pain outcomes and scores on the PCS, TSK, CPAQ, MAIA, and FFMQ using regression models.

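### EMA is to be vetted as a trial outcome, but Hypothesis 4 plans a correlation best read as one of levels, and no analysis relates EMA change to questionnaire change

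*SAP*

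**What the plan says.** Specific Aim 2 (Protocol section 7.2) sets the purpose: "We will compare pain questionnaires and EMA and ensure that an EMA measure is refined and vetted before use as a clinical trial outcome".

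SAP Hypothesis 4 gives the quantitative comparison: "We will assess the correlation of our EMA measures with the Numeric Pain Rating Scale for pain intensity, and pain interference rating". It continues: "We predict a correlation of >.7". It does not say which week is used, whether scores are levels or changes, how repeated EMA ratings are summarised per person, or whether an interval is reported. A qualitative part follows: "We will also perform qualitative assessment to get participants assessment of where the two approaches are similar", and where they may differ.

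SAP Hypothesis 3 models "changes in pain interference at the end of the intervention and at 6-month follow-up (separate for EMA and questionnaires", and reports Cohen's d "with 95% confidence intervals, based on standard deviation at baseline". It places the EMA ratings by day and week: "rating on day 1-7 in week 1 or 8 of intervention". Protocol section 7.9 (Schedule of Measures) places the questionnaires in the first and last course weeks and at 6 months. Both instruments are therefore available in weeks 1 and 8.

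SAP Hypothesis 6 refers explicitly to changes in pain outcomes when it plans its correlations. Hypothesis 4 has no such word, so levels are the plain reading.

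**The concern.** A trial outcome has to register change. A correlation of levels between two pain measures is driven largely by stable differences between people: those with more pain score higher on both. It can be high even when one measure follows change in individuals poorly.

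Hypothesis 3 covers part of this, because it estimates average change on each instrument. It asks whether participants improve, however, not whether EMA and questionnaire agree about who improved and by how much. It is not linked to the vetting aim, and the two sets of results are not compared. A later trial could therefore take up an EMA outcome on the strength of a level correlation and a plausible mean shift, with no evidence that it follows individual change.

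**Working it through.** **1. The plan's own correlation figure.** The monitoring plan in the protocol (its section 6.2) states 80% power at n = 40, two-sided alpha 0.05, for a Pearson correlation of 0.43 between change scores. With Fisher's z, power = Φ(atanh(0.43) × √37 − 1.96) = Φ(2.797 − 1.960) = 79.9%. It reproduces. It was not set for Hypothesis 4, whose .7 has no derivation, but it gives the only sample size stated for a correlation: 40 MBPR participants. (Protocol section 9.3 calls the same 0.43 a coefficient of determination. On that reading power would be about 99.8%, so the label needs reconciling.)

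**2. What a level correlation implies about change.** Assume equal variances at both weeks and the same retest correlation ρ for both measures. Let r be the same-week correlation of EMA with questionnaire, and c their correlation across weeks. Then

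r_change = (r − c) / (1 − ρ).

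This is zero when c = r. The correlation matrix remains valid provided r + c ≤ 1 + ρ, so zero change correlation is possible when ρ ≥ 2r − 1:

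- r = .70 needs ρ ≥ .40
- r = .75 needs ρ ≥ .50
- r = .80 needs ρ ≥ .60

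The documents give no retest correlation, so ρ is an assumption.

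**3. Illustration, all variances assumed.** Stable pain level has variance 1, individual change variance 0.25, questionnaire error 0.20, EMA error 0.10, and mean change is −0.5. Take an EMA that ignores change altogether:

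- Week-1 level correlation: 1/√(1.20 × 1.10) = 0.87
- Week-8 level correlation: 1/√(1.45 × 1.10) = 0.79
- Change correlation: 0

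In 20,000 simulated samples of 40, the level correlation exceeds .7 in 99.8% (week 1), 91% (week 8) and 97% (weeks pooled). With change variance from 0.1 to 0.5 and questionnaire error from 0.1 to 0.3, the week-8 level correlation runs from 0.71 to 0.87, still with zero change correlation.

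**4. What Hypothesis 3 would show.** For this EMA, d is 0.00. The questionnaire has d = −0.5/√1.20 = −0.46 (simulated mean −0.47 at n = 40), so total failure to respond is visible. Now add the same −0.5 to everyone's week-8 EMA. Correlations within a week do not move when a constant is added, so the level results stand and the change correlation stays 0. EMA's d becomes −0.5/√1.10 = −0.48, next to −0.46. Both hypotheses look satisfied.

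**5. Precision (Fisher z, 95%).**

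| n | observed level r = .70 | half-width near change r = 0 |
|---|---|---|
| 36 (10% loss) | 0.48 to 0.84 | 0.33 |
| 40 | 0.50 to 0.83 | 0.31 |

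If the MBSR participants were included (n = 50), the first interval would be 0.52 to 0.82. At n = 40 the lower limit exceeds .7 only from an observed r of tanh(0.867 + 1.96/√37) = 0.83. If the true value is 0.6, the estimate exceeds .7 with probability 1 − Φ((0.867 − 0.693) × √37) = about 14%. An observed change correlation of 0.50 at n = 40 has CI 0.22 to 0.70.

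**6. Comparability of the two d values.** The baseline SD is not defined for EMA. If it were the SD of single ratings, with equal within- and between-person SD and 20 ratings a week (both assumed; Protocol section 15.3 pays $1 per response up to $40 over two weeks), d would be √(1 + 1/20)/√2 = 0.72 of its value on person means. EMA would look less responsive for arithmetic reasons alone.

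**The case against.** The strongest reply is that responsiveness is already covered. Hypothesis 3 estimates change on both instruments with effect sizes and intervals, and Hypothesis 4 adds a qualitative comparison. That stands for average change. A reader might infer that the level correlation is the only evidence planned on EMA, or that responsiveness goes unexamined; the documents do not support either. What is missing is the link between the two changes.

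Second, .7 is a prediction. A reader might take it as a pass mark for adopting EMA, but nothing in the SAP makes adoption depend on it. Nor does the SAP say that the future primary outcomes will be collected by EMA, so harm to a later trial is possible but not established.

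Third, a low change correlation is ambiguous. Suppose each instrument equals true pain (variance 0.75) plus independent error (variance 0.25), and true pain correlates 0.933 across weeks. Then same-week r = 0.75, and the retest and cross-week correlations are both 0.75 × 0.933 = 0.70. The change correlation is 0.05/0.30 = 0.17, although both instruments follow true pain fully. In the illustration in step 3, an EMA that follows change completely reaches only 0.25/√(0.65 × 0.45) = 0.46. This stands, and limits how the added statistic may be read.

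Finally, the sample is small and pools MBPR iterations that differ by design. That argues for an interval and modest claims. It does not argue for omission, since the monitoring plan already foresees change-score correlations at n = 40.

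**Conclusion.** The point holds in a limited form. The plan's quantitative check of EMA against questionnaires is a correlation most naturally read as one of levels, with no week or interval given, and no analysis relates EMA change to questionnaire change. Hypothesis 3 would expose an EMA that does not respond at all. It would not expose one with the right mean shift that fails to follow individuals.

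The compatibility of r = .70 with zero change correlation rests on equal variances and a retest correlation of at least .40, and the illustration rests on assumed variances. They show what the planned check cannot exclude, not that this EMA is unresponsive. Reading Hypothesis 4 as levels is itself an inference from its wording beside Hypothesis 6; if change was meant, the text still has to say so. The interval of 0.50 to 0.83 assumes 40 complete pairs.

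This is an inexpensive improvement that bears directly on Aim 2. It does not undermine the feasibility study.

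**What to change.** Add to Hypothesis 4:

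1. The correlation of EMA change (week 8 minus week 1, using each person's mean for the week) with questionnaire change, for intensity and for interference, with 95% CI.
2. The standardised changes from Hypothesis 3 for EMA and questionnaire side by side, both standardised on the SD of week-1 person-level scores.
3. The level correlation at week 1 and at week 8 separately, one pair per person, with 95% CI beside the .7 prediction.

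State which participants enter. State also that a low value in (1) may reflect questionnaire error or little true change, so it is to be read with (2) and does not alone count against EMA.

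The cost is SAP wording and one table; no new data are needed. The drawback is imprecision in (1): a half-width of about 0.31 near zero at n = 40.
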